9.7.1. Contact with the Sponsor

The names and contact telephone numbers of representatives of Cellavita Pesquisa Científica LTDA, the Principal Investigator, among others, are listed in item III of this protocol and will be made available to participants.

10. ETHICAL AND REGULATORY CONSIDERATIONS

This Protocol will be conducted in accordance with the guidelines of the International Conference on Harmonization - ICH for Good Clinical Practices and Document of the Americas, as well as national and international legislation.

The Research Center with its Investigators, sub-investigators, study coordinators and internal monitors declare that the protocol and the Informed Consent Form will be conducted in accordance with current ICH GCP and in accordance with applicable local regulations (Resolution No. 466 of December 12, 2012, Resolution No. 251 of August 7, 1997) of the CNS-MS.

10.1. Declaration of the Americas and Regulation

The study will be conducted in accordance with resolutions 466/12 and 251/97 of the National Health Council/MS, respecting mainly the participant and the Good Clinical Practices/Document of the Americas.

10.2. Belmonte Communication

The study will comply with the guidelines of ethical conduct of the Belmonte Communication, which has 3 basic principles:

- a) Respect;
- b) Beneficence;
- c) Justice.

10.3. Informed Consent Form (ICF) and Image Authorization Term

The Investigator will protect the integrity of the participants by following all applicable regulations. These regulations are made available upon Sponsor's request. The ICF used during the consent-obtainment process must be reviewed by Sponsor, approved by CEP and made available for inspection.

Before any procedure required by the protocol is performed, the participant must:

- Be informed of all relevant aspects of the study and the elements of informed consent.
- Have enough time to resolve doubts and think about the decision to participate.

- Voluntarily agree to participate in the study.
- Sign and date an informed consent form approved by the CEP.

The Image Authorization Term must be signed for participants who allow them to be filmed for scientific purposes. The same standards of Good Clinical Practice so followed for obtaining the ICF will apply to this term as well.

10.4. Risks and benefits

The risks involving the drugs in the study are: rejection of the administered cells, susceptibility to opportunistic diseases, grafting of cells in an unwanted place, unwanted biological effect (in vivo differentiation in unwanted cell types), toxicity (infusion or systemic) (symptoms: transient fever, bronchospasm and/or laryngospasm, chills, diarrhea, dyspnea, headache, facial edema, glottis and/or larynx, fever, hemoglobin, hypotension, nausea, itching, facial flushing, abnormal bleeding, sweating, tachycardia, dizziness, hives and vomiting), toxicity to DMSO (symptoms: cough, flushing, rash, chest tightening and wheezing, nausea and vomiting, cardiovascular instability), formation of neoplasms (malignant or benign), transmission of diseases, reactivation of latent viruses, unwanted immune response, cellular contamination (with unwanted cells, components of the culture media or chemical compounds), mixture of autologous material of the patient, cardiac, vascular, renal, neurological, pulmonary, hematological or hepatic dysfunctions (malignant or benign).

When applicable, adverse events will be minimized and if they evolve it will be the responsibility of the Sponsor of the study to follow-up the participant until the solution thereof.

The potential benefits of the investigational product are the reduction of neuronal loss and the stimulation of neurogenesis of both endogenous and newly transplanted cells, activating a neuroprotective environment that is able to integrate new cells and replace dead neural cells or in the process of apoptosis. Therefore, cell therapy could be able to delay the onset or course of pathology, which would represent a major advance for these patients (Fink et al., 2015).

Based on these data and due to the devastating and fatal nature of the disease, it is possible to observe that the benefits presented in this study outweigh the possible risks involved.

10.5. Preserving the identity of research participants

In the process of maintaining the right of the participants' privacy, each participant will be codified at the time of inclusion and this code should be used in the study documentation.

10.6. Post-study drug supply

Sponsor understands and is aware of the foregoing in item III.3.d of CNS Resolution N. 466/2012 that all participants are assured, at the end of the study, to get free and indefinite access to the best therapeutic methods that prove effective. Sponsor is also aware of sub-item d1 that access will be guaranteed in the interval between the end of individual participation and the end of the study, and in this case, this warranty can be given through an extension study, according to the duly justified analysis of the participant's attending physician.

The benefit weighting of the investigational product is done in two distinct ways: collectively or individually. The individual benefit analysis is performed when the participant terminates his/her participation in the study, and not when the research is completed. If the investigational product has proved beneficial to the individual, the product must be supplied for as long as necessary (guarantee of continuity). The definition of the individual benefit is not the exclusive prerogative of the study physician and can also be performed by the participant's personal physician (assistant). The collective benefit is that defined in interim or final analyses, when it is possible to conclude whether the investigational product proved beneficial, or not, to the experimental group. In this case, the supply of the investigational product should also extend to the control group.

Thus, in the event of individual benefit, Sponsor shall ensure the provision of the investigational product free of charge, if efficacy is demonstrated, and this is a weighting of the study physician or personal physician. Furthermore, in the case of collective benefit, Sponsor shall ensure, free of charge, the investigational product to all participants of the research if collective benefit is observed, identified in interim analysis or at the end of the study. Therefore, Sponsor undertakes, before the Brazilian regulatory authorities, to ensure access to the investigational product of the study to all participants who participate in this study (for both discontinued or non-discontinued participants), according to the commitment established in the Informed

Consent Form, and according to the judgment/prescription of the Investigator and/or clinical team.

Access to the study medication will be ensured for as long as necessary at the discretion of the physician, or in case the treatment is replaced or presents any safety-related problems.

10.7. Declaration of interest

The Research Center with its Investigators and sub-investigators declare absence of any conflict of interest.

10.8. Ethics and publication policy

Sponsor's policy is to publish or otherwise communicate the results of its clinical case-checking and exploratory studies, whatever the evolution, for marketed products, compound(s) or research product(s) subsequently approved for commercialization.

Clinical hypothesis test studies are those that aim to provide significant results through the analysis of pre-specified questions, using statistically valid predefined plans for data analysis, thus providing strong evidence of safety and/or efficacy to corroborate their claims about the products.

On the other hand, exploratory studies serve to determine the direction of possible future studies. They have significant statistical limitations, provide only preliminary information about a disease, condition, or product, and are not designed to provide final conclusions about product claims.

Therefore, in accordance with Resolution 466/12, Sponsor declares that the search results will be made public, whether favorable or not.

11. PROTOCOL CHANGES

11.1. Amendments

Any change in the study plan requires an amendment to the protocol. The Investigator shall not make any changes to the study without the approval of the CEP and Sponsor, except where necessary to eliminate immediate obvious risks to participants. An amendment to the protocol to eliminate an immediate obvious risk to participants can be promptly implemented, but the change must then be documented in an amendment, informed to the CEP within 5 working days, and forwarded to the regulatory agency within the required time frame. All amendments to the protocol must be analyzed and approved, following the same process as the original protocol.

11.2. Amendment submission

The amendments, in the context of RDC 09/2015, are defined as any changes made to the clinical protocol, whether substantial or not, and it is at Sponsor's discretion to evaluate in which of these categories it will fit and its impact on clinical development.

Substantial amendments are considered those that interfere with the safety, physical or mental integrity of research participants, as well as significant changes in the scientific value of the clinical trial protocol, such as the change from a placebo comparator to an active comparator, insertion of additional experimental arms, or changes in the statistical analysis plan. On the other hand, non-substantial amendments are those that do not entail alterations relevant to the scientific value of the protocol, such as small clarifications, spelling correction, among others.

All amendments (substantial or non-substantial) must be submitted to the country CEP at the same time. However, substantial amendments must wait for both ethical assessment and manifestation of CONEP to be implemented to the protocol already presented, while non-substantial ones can be promptly implemented, being only described as part of the annual report of the clinical trial.

11.3. Deviations and protocol violations

Deviation from protocol: any lack of compliance with the procedures or requirements defined in the version of the protocol approved by the Research Ethics

Committee (CEP) without major implications for the integrity of the study, the quality of the data or the rights and safety of the participants.

Violation of protocol: deviation from the protocol that may affect the quality of the data, that compromises the integrity of the study or that may affect the safety or rights of participants.

In general, a significant deviation from the protocol is considered as a violation of the protocol, while a minor deviation is considered as a deviation from the protocol.

Any deviation from the original statistical plan shall be described and justified in the protocol and/or final report, if appropriate. Table 06 exemplifies the significant deviations from the protocol and the necessary actions and documentation.

Table 06. Model of protocol deviations and corrective actions.

Significant Deviations from the Protocol	Action/Documentation Required
Some Baseline procedure was performed after the administration of the medication under study	The deviation must be notified by the monitor via the Protocol Deviations form. In addition, the reason for the deviation should be documented in the participant's medical records.
Deviations from inclusion and exclusion criteria	When this type of deviation is found after randomization, the study team should be notified to determine whether the participant should remain in the study. The reason for the deviation should be documented in the participant's medical records.
Variance in The Statistical Test to Be Used	Any deviation from the Statistical Test to be used must be thoroughly justified in the final report.

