8.8.1. Deviations from the Original Statistical Plan

Any deviation from the original statistical plan shall be described and justified in the protocol and/or final statistical report, where appropriate.

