#### 7.6. Change from the Analysis Plan in Protocol

The analysis described in this SAP supersedes what was in the protocol as it was deemed more appropriate based on the data collected in the study and analysis methods for studies in Huntington's disease.

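### Protocol 11.1–11.2 require an approved amendment to change the statistical plan; 8.8.1, 11.3 and Table 06 ask only for a justification, and nothing locks the primary test before unblinding

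*Protocol*

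**What the plan says.** **Rules that require prior approval.** Protocol 11.1: "Any change in the study plan requires an amendment to the protocol". Protocol 11.2 gives examples of substantial amendments, among them "insertion of additional experimental arms, or changes in the statistical analysis plan", and adds that "substantial amendments must wait for both ethical assessment and manifestation of CONEP to be implemented to the protocol already presented". The same section leaves it to the sponsor to decide which category an amendment falls in.

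**Rules that require only a justification.** Protocol 8.8.1: "Any deviation from the original statistical plan shall be described and justified in the protocol and/or final statistical report, where appropriate". Protocol 11.3 repeats it: "Any deviation from the original statistical plan shall be described and justified in the protocol and/or final report, if appropriate". Table 06 lists a variance in the statistical test as a significant deviation, and the action it gives is: "Any deviation from the Statistical Test to be used must be thoroughly justified in the final report".

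**What the SAP does.** Version 1.0 is dated 16 March 2022 and is the only entry in its history. Section 1 says it is based on Amendment 6 (23 February 2021), that it departs from the protocol's statistical section, and that the clinical study report will identify the changes. Section 7.6 says the SAP analysis "supersedes what was in the protocol as it was deemed more appropriate based on the data collected in the study", and goes on to cite methods used in Huntington's disease studies. Section 4.1.2 reports the V11 MRI in the past tense for all participants. Section 7.4.1 allows the primary model to be altered or other models to be run, because of the small sample and COVID-19 disruption to visits, without naming the alternatives, a trigger or a date.

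**The concern.** A final report is written once results are known. A rule that lets a changed test be explained there, with no date by which the change must be made and no duty to show the planned test, does not stop the primary analysis from being chosen with results in hand. If that happened, the 5% level in SAP 5 would no longer describe the test reported, and a positive result could not be told apart from selection. Protocol 10.8 ties strong evidence to "using statistically valid predefined plans for data analysis". The trial has 35 participants, 7 of them on placebo, and one primary comparison, so that comparison's credibility rests largely on its having been fixed in advance.

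**Working it through.** The protocol states no figure on this point. The main check is of the text; the arithmetic gives scale only.

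**Step 1. The rules side by side.**

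| Place | Trigger | Required | Timing |
|---|---|---|---|
| Protocol 11.1 | Any change in the study plan | Amendment, with ethics committee and sponsor approval | Before, except for immediate risk to participants |
| Protocol 11.2 | Change in the statistical analysis plan (named example) | Substantial amendment | After ethical assessment and CONEP's response |
| Protocol 8.8.1 | Deviation from the statistical plan | Justification in protocol and/or final statistical report | None stated |
| Protocol 11.3, text | Same | Justification in protocol and/or final report | None stated |
| Protocol 11.3, Table 06 | Different statistical test | Justification in final report | None stated |
| Protocol 14.1 | Protocol violation | Notify the ethics committee | Notice, not approval |

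The lower rows do not refer to 11.2, and none mentions database freeze or unblinding.

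**Step 2. What changed between protocol and SAP.**

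| | Protocol 8.7.1.1.1 | SAP 5 and 7.4.1 |
|---|---|---|
| Response | UHDRS motor score at the end of three cycles | TMS slope per year, baseline to V11 |
| Comparison | Treatment as a factor | Two doses pooled against placebo (primary) |
| Model | Linear, baseline-adjusted | MMRM with treatment, baseline TMS and treatment by day |
| Multiple comparisons | Corrected | No correction stated; every test at two-sided 5% |

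This is a change in the primary analysis, the kind of change that 11.2 sends to prior review.

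**Step 3. Scale.** With no treatment effect, and two tests each at level 0.05, the chance that at least one rejects is 0.05 + 0.05 − P(both reject). It is 0.05 if the tests always agree and 1 − 0.95² = 0.0975 if they are independent. Where it falls between depends on their correlation, which was simulated.

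Assumptions, none from the documents: baseline mean 30 and SD 12, mean slope 4 points per year, normal errors. Design: groups of 7, 14 and 14, and 12 visits 30 days apart (V0 to V11). Test A is the three-group baseline-adjusted model at V11. Test B compares baseline-adjusted per-participant slopes, pooled doses against placebo, as a stand-in for the MMRM. There were 4,000 null trials per setting.

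| Slope SD per year | Visit noise SD | A alone | B alone | A or B | Implied P(both) |
|---|---|---|---|---|---|
| 2 | 3 | 0.050 | 0.046 | 0.088 | 0.050 + 0.046 − 0.088 = 0.008 |
| 4 | 3 | 0.050 | 0.048 | 0.082 | 0.016 |
| 4 | 5 | 0.043 | 0.050 | 0.084 | 0.009 |
| 6 | 3 | 0.051 | 0.052 | 0.082 | 0.021 |

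The Monte Carlo standard error is about √(0.085 × 0.915 / 4000) = 0.004. A second run with other assumed values (baseline SD 10, slope SD 3–8, noise SD 2–4; 6,000 trials per setting) gave 0.079 to 0.086. Both runs put the error at about 8–9%. Relative to the stated level, the first run gives 0.082/0.05 = 1.6 to 0.088/0.05 = 1.8 times. With one test fixed before unblinding, it stays at 0.05.

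**The case against.** **The sections can be read together.** Sections 11.1–11.2 govern changes to the plan; 11.3 says how to record non-compliance. The other Table 06 rows (late baseline procedures, eligibility breaches) are not permissions, so the third need not be one. Its entries are significant deviations, which 11.3 generally treats as violations, and 14.1 requires notice of violations to the ethics committee. This stands in part: Table 06 does not authorise a swap, and justification is not the only consequence. But choosing another test is a deliberate decision, not an event discovered afterwards, and nothing sends it back to 11.2.

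**Table 06 says where a change is justified, not when it is decided.** That is correct, so a reader who infers that the test may be, or was, changed after results were seen goes further than the text. Protocol 6.5 blinds the statistician and data manager, and 8.10 rules out interim analysis. Both lower the risk during the trial. The first protection is weaker than it looks: under 6.4 and 6.6 the person responsible for the statistical analysis generates the randomisation list and forwards it to the sponsor.

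**The SAP gives other reasons.** A reader might take the reference to data collected as an admission of outcome-driven choice. The same sentence cites disease-specific methods, section 1 cites other HD studies, and 7.4.1 cites sample size and COVID-19. The phrase may mean the type and timing of the data. Nothing shows that results by arm were known.

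**Filing and code status.** A reader might also infer that no amendment was filed. The documents show only that the SAP was based on Amendment 6. V11 scans in the past tense suggest that follow-up was finished, not that the code was open.

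**The trial is exploratory.** Section 10.8 recognises exploratory studies, and 8.1 gives the sample size a non-statistical basis. SAP 5 nonetheless sets formal tests at two-sided 5%, so the level has to mean what it says.

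**Conclusion.** The change-control text is wrong as written. One set of sections requires prior approval for changes in the statistical plan, another accepts a justification with no date, and no section of either document fixes the primary test before the code is opened. The SAP has since replaced the primary analysis, leaves it to the clinical study report to identify the changes, and keeps the model open.

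The size is a type I error of about 8–9% against a stated 5%. This rests on assumed variances, on a per-participant slope standing in for the MMRM, and on choosing the smaller p-value after seeing both. It is what the rules fail to prevent, not something shown to have occurred.

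Larger figures should not be charged to this rule. Adding each dose against placebo gave 10–11%, but the SAP lists those tests openly and names the pooled one as primary, so that is dose-level multiplicity. Adding the two baselines in protocol 8.3 gave 13–15%, but that is a separate ambiguity.

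**What to change.** 1. In protocol 8.8.1, 11.3 and Table 06, state that a change to the primary endpoint, population, model or test follows 11.2 and is dated before the randomisation code is opened. Any later change is labelled post hoc and reported beside the planned test.
2. In SAP 7.4.1, delete the sentence that leaves the model open, or replace it with named alternatives and triggers fixed before unblinding. Rewording Table 06 alone would leave this gap.
3. File the SAP change as an amendment before the code is opened, and report the protocol 8.7.1.1.1 model beside the SAP slope. If the code was already open, label the slope analysis post hoc and report the protocol-planned analysis. In that case the motor model should not be called the sole pre-specified result: the synopsis, 3.1.1 and 8.3 name the UHDRS across its domains as the primary variable, while 8.7.1.1.1 models the motor score. The report should state that conflict.

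Cost: one amendment, one or two extra tables, and a possible post hoc label on the SAP slope result.

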12. SUSPENSION, CLOSURE AND COMPLETION OF THE STUDY

Sponsor may suspend or terminate a study, or part of it, at any time for any reason. After the decision of suspension or cancellation, Sponsor shall notify the CEP within a maximum of 15 calendar days, except in cases of temporary suspension as a security measure, when the period is 7 calendar days from the date of suspension. It is emphasized that cancellations under RDC 09/2015 are definitive and apply only to clinical trial protocols already initiated, with no possibility of subsequent reactivation.

If the Investigator suspends or terminates the study, he/she shall inform Sponsor and CEP immediately and provide them with detailed written information. The Investigator will also return to Sponsor all products under investigation, their containers and other study materials. At the time of completion of the study, the Researcher will provide Sponsor and CEP the final reports and abstracts, as required by current regulations.

Clinical Protocol: ADORE-DH Sponsor: Cellavita Pesquisa Científica LTDA Amendment 6 dated February 23, 2021.

13. QUALITY CONTROL

Sponsor performs quality control and warranty checks on all clinical studies that it sponsors. Before including any participant in this study, the Sponsor team and the Investigator review the protocol, the Investigator's Brochure, the CRF's and the instructions for its completion, the procedure for obtaining informed consent, and the procedure for reporting AEs and SAEs. A qualified Sponsor representative will monitor the conduct of the study. During these visits to the centers, the information recorded in the CRF's will be compared with the source documents.

